9.4.1.4 Control of Experiment-wise Type 1 Error

Not applicable because the statistical test for the primary analysis of the primary endpoint is performed only once, which is comparison of the OPC-64005 20-mg group with the placebo group.

9.4.1.5 Other Efficacy Endpoint Analysis

Not applicable.

9.4.2 Safety Analysis

The safety analysis will be performed on the safety analysis set. Baseline is the last data obtained after the start of IMP administration in the placebo lead-in period and before the start of double-blind IMP administration.

9.4.2.1 Adverse Events

All AEs will be coded by system organ class and ICH's Medical Dictionary for Regulatory Activities (MedDRA) preferred term. The incidence of the following events will be summarized by treatment group and for the overall OPC-64005 group:

- TEAEs
- TEAEs by severity
- TEAEs with an outcome of death
- Serious TEAEs
- TEAEs leading to discontinuation of the IMP
- TEAEs of special interest (drug eruption)

Treatment-emergent AEs potentially causally related to the IMP will also be summarized in the same manner.

9.4.2.2 Clinical Laboratory Data

Descriptive statistics of measurement values and changes from baseline at each time point will be calculated by treatment group and for the overall OPC-64005 group for each laboratory test item of continuous data.

Each laboratory test item of continuous data will be classified into below the lower limit of the reference range, within the reference range, or above the upper limit of the reference range based on the reference ranges of the central laboratory, and a shift table from baseline will be generated by treatment group and for the overall OPC-64005 group.

For each laboratory test item of qualitative data, a shift table from baseline will be generated by treatment group and for the overall OPC-64005 group.

The number and proportion of subjects who meet the criteria for clinically significant laboratory value will be determined by treatment group and for the overall OPC-64005 group.

9.4.2.3 Physical Examination and Vital Signs Data

For each item of vital signs (by position for blood pressure and pulse rate), descriptive statistics of measurement values and changes from baseline at each time point will be calculated by treatment group and for the overall OPC-64005 group.

The number and proportion of subjects who meet the criteria for clinically significant vital signs will be determined by treatment group and for the overall OPC-64005 group.

9.4.2.4 Electrocardiogram Data

For heart rate, PR interval, RR interval, QRS interval, QT interval, and QTc (QTcF), descriptive statistics of measurement values and changes from baseline at each time point will be calculated by treatment group and for the overall OPC-64005 group.

For normal/abnormal assessment of 12-lead ECG, a shift table from baseline will be generated by treatment group and for the overall OPC-64005 group.

For QTc (QTcF) at each time point, the number and proportion of subjects with measurement values after double-blind IMP treatment of > 450 msec, > 480 msec, and > 500 msec, and the number and proportion of subjects with changes from baseline of > 30 msec and > 60 msec will be calculated by treatment group and for the overall OPC-64005 group.

The number and proportion of subjects who meet the criteria for clinically significant ECG will be determined by treatment group and for the overall OPC-64005 group.

9.4.2.5 Other Safety Data

Body weight, body mass index (BMI) and waist circumference
 For body weight, BMI, and waist circumference, descriptive statistics of
 measurement values and changes from baseline at each time point will be calculated
 by treatment group and for the overall OPC-64005 group.
 An analysis of the ANCOVA model with treatment group as a factor and baseline as
 a covariate will be performed using the LOCF dataset. The least square means of each
 treatment group and the differences in the least square means between each OPC 64005 group and the placebo group, as well as the two-sided 95% CIs, will be

The number and proportion of subjects who meet the criteria for clinically significant body weight will be determined by treatment group and for the overall OPC-64005 group.

calculated.

C-SSRS

The number and proportion of subjects at each time point will be calculated by treatment group and for the overall OPC-64005 group for each item (suicidality, suicidal ideation, suicidal behavior, completed suicide, emergence of suicidal ideation, emergence of serious suicidal ideation, worsening of suicidal ideation, and emergence of suicidal behavior).

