1.3 Schedule of Assessments

Table 1.3-1	Schedule	of Assess	sments									
Period	Screening	Placebo Lead-in ^a				olind Trea				Double- blind Tapering	Post- treatment Observation ^j	At Discontinuation ^l
Visit	Visit 1	Visit 2 (Week -1)	Visit 3 (Baseline)	Visit 4 (Week 1)	Visit 5 (Week 2)	Visit 6 (Week 3)	Visit 7 (Week 4)	Visit 8 (Week 5)	Visit 9 (Week 6)	Visit 10 (Week 7)	Visit 11 (2 weeks after Visit 10 or the final dosing)	
Day ± allowable window	Day -35 to the day before Visit 2	Day -7 ± 1 day	Day 1	Day 8 ± 1 day	Day 15 ± 2 days	Day 22 ± 2 days	Day 29 ± 2 days	Day 36 ± 2 days	Day 43 ± 2 days	Day 50 ± 2 days	14 days ± 7 days after Visit 10 or the final dosing	
Informed consent	•											
Demographics	•											
Concomitant	4											
medications/therapies												
Eligibility assessment	•	•	•									
Randomization			•									
MADRS	•	•	•	•	•	•	•	•	•			•
CGI-I				•	•	•	•	•	•			• ¹
CGI-S	•	•	•	•	•	•	•	•	•			•
HAM-D	•	•	•						•			•
MADRS-S	•	•	•	•	•	•	•	•	•			•
Apathy Scale			•						•			•
Laboratory tests b	•		•						•			•
Vital signs ^c	•	•	•	•	•	•	•	•	•	•		•
Physical examination	•	•	•	•	•	•	•	•	•	•	•	•
Height ^d and body weight, waist circumference	•		•						•			•
12-lead ECG	•		•		•		•		•			•

Table 1.3-1	Schedule of Assessments											
Period	Screening	Placebo Lead-in ^a			Double-k	olind Trea	ntment			Double- blind Tapering	Post- treatment Observation ^j	At Discontinuation k
Visit	Visit 1	Visit 2 (Week -1)	Visit 3 (Baseline)	Visit 4 (Week 1)	Visit 5 (Week 2)	Visit 6 (Week 3)	Visit 7 (Week 4)	Visit 8 (Week 5)	Visit 9 (Week 6)	Visit 10 (Week 7)	Visit 11 (2 weeks after Visit 10 or the final dosing)	
Day ± allowable window	Day -35 to the day before Visit 2	Day -7 ± 1 day	Day 1	Day 8 ± 1 day	Day 15 ± 2 days	Day 22 ± 2 days	Day 29 ± 2 days	Day 36 ± 2 days	Day 43 ± 2 days	Day 50 ± 2 days	14 days ± 7 days after Visit 10 or the final dosing	
Pregnancy test ^e	•	•								•		•
C-SSRS	•	•	•	•	•	•	•	•	•	•	•	•
AEs	•											•
Blood sampling for plasma PK assessment f				•	•		•		•			
Blood sampling for CYP2D6 genetic testing			● ^h									
Blood sampling for DNA storage ^g			● ^h									
IMP dispensing ⁱ		•	•	•	•	•	•	•	•			•
IMP compliance			•	•	•	•	•	•	•	•		•

^aThe placebo lead-in period is conducted in a single-blind manner with subjects blinded to treatment received.

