In Trial 277-201-00001, on the other hand, the incidence of AEs that led to discontinuation of the trial in the OPC-64005 group was 23.4% (18/77 subjects) and higher than that in the placebo group (8.5%, 7/85 subjects). Most of these AEs occurred during the early stage of treatment initiation (during treatment at 20 mg). Therefore, in consideration of safety at an early stage of treatment, the starting dose in the present trial was set at 10 mg, which is lower than the starting dose of Trial 227-201-00001.

As of Oct 2019, there are no TRIs approved in Japan or overseas, and the safety profile is unknown. The 10-mg group was also included in the trial because evaluation of safety at the lower dose is beneficial when assessing the safety profile of OPC-64005.

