5.3 Handling of Missing Data

For the primary endpoint analysis, a mixed-model repeated measures (MMRM) analysis will be performed using the observed cases (OC) dataset without imputation of missing data on an assumption of missing at random (MAR). Placebo multiple imputation and tipping point analysis on an assumption of missing not at random (MNAR) will be performed as a sensitivity analysis for handling of missing data.

The secondary endpoint analyses (MADRS response rate, MADRS remission rate, Clinical Global Impression – Improvement [CGI-I] improvement rate, CGI-I score, mean change from baseline in HAM-D 17-item total score, and mean change from baseline in Apathy Scale total score) and the safety analysis (body weight, body mass index [BMI], and waist circumference) will be performed using data imputed with the last data after the start of double-blind IMP administration (last observation carried forward [LOCF]).

6 Primary and Secondary Outcome Variables

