8.2 Secondary Efficacy Analyses

The secondary endpoint analysis will be performed on the FAS.

- MADRS response rate
- MADRS remission rate
- CGI-I improvement rate

The MADRS response rate in the OPC-64005 20-mg group will be compared with that in the placebo group using the χ^2 test in the LOCF dataset. The differences in the response rates between each OPC-64005 group and the placebo group, as well as the two-sided 95% CI (Wald confidence interval), will be determined. The MADRS remission rate and CGI-I improvement rate will be analyzed in the same manner as the MADRS response rate. The same analysis will be performed on the OC dataset.

- Mean change from baseline in HAM-D 17-item total score
- Mean change from baseline in Apathy Scale score

An analysis will be performed on the mean change from baseline in HAM-D 17-item total score using the analysis of covariance (ANCOVA) model with treatment group as a factor and baseline as a covariate in the LOCF dataset. The least square means of each treatment group and the difference in the least square means between each OPC-64005 group and the placebo group, as well as the two-sided 95% CIs, will be calculated. The mean change from baseline in Apathy Scale total score will be analyzed in the same manner as the mean change from baseline in HAM-D 17-item total score. The same analysis will be performed on the OC dataset.

- Mean change from baseline in CGI-S
- Mean change from baseline in MADRS-S total score (total score of Items 1 through 9)
- Mean change from baseline in MADRS anhedonia factor score (total score of MADRS Items 1, 2, 6, 7, and 8)

The MMRM analysis will be performed in the same manner as that for the primary endpoint.

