9.7 Other Safety Data

9.7.1 Body Weight, Body Mass Index, and Waist Circumference

For body weight, BMI, and waist circumference, descriptive statistics of measurement values and changes from baseline at each time point and the last time point (LOCF; Week 6 in the double-blind treatment period) will be calculated by treatment group and for the overall OPC-64005 group.

An analysis of the ANCOVA model with treatment group as a factor and baseline as a covariate will be performed. The least square means of each treatment group and the differences in the least square means between each OPC-64005 group and the placebo group, as well as the two-sided 95% CIs, will be calculated.

The number and proportion of subjects who meet the criteria for clinically significant body weight (Appendix 1) will be determined by treatment group and for the overall OPC-64005 group. The same analysis will also be performed by baseline BMI category (< 18.5, \geq 18.5 to < 25, \geq 25 to < 30, \geq 30). A listing of subjects who meet the criteria for clinically significant body weight (Appendix 1) will be provided.

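### The only modelled safety comparison (weight, BMI, waist) is fitted to LOCF values treated as Week 6, with no observed-case companion, so its adjusted difference mixes exposure durations

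*Protocol*

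**What the plan says.** **Model.** Protocol 9.4.2.5 plans an ANCOVA for body weight, BMI and waist circumference, with treatment group as factor and baseline as covariate, on carried-forward data: "a covariate will be performed using the LOCF dataset". It gives least square means, differences from placebo and 95% confidence intervals. SAP 9.7.1 repeats the model without naming a dataset, but SAP 5.3 settles the question: "the safety analysis (body weight, body mass index [BMI], and waist circumference) will be performed using data imputed with the last data".

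**Label.** In its sentence on descriptive statistics, SAP 9.7.1 identifies the carried-forward endpoint with Week 6: "the last time point (LOCF; Week 6 in the double-blind treatment period) will be calculated by treatment group".

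**Measurement times.** In the schedule of assessments (Protocol 1.3), weight and waist are taken at screening, baseline, Visit 9 (Week 6) and discontinuation.

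**Other summaries of the same variables.** Protocol 9.4.2.5 also plans descriptive statistics ("measurement values and changes from baseline at each time point will be calculated") by group. SAP 9.7.1 keeps these and adds counts of clinically significant weight, overall and by baseline BMI category, with a subject listing.

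**Other LOCF analyses.** For response, remission, CGI-I improvement, HAM-D and Apathy Scale, SAP 8.2 adds: "The same analysis will be performed on the OC dataset". SAP 8.4 does the same for the CGI-I score. SAP 9.7.1 contains no such sentence.

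**The concern.** All other safety data are handled with descriptive statistics, shift tables, counts and listings. This ANCOVA is therefore the only place where a safety variable gets a baseline-adjusted difference from placebo with a confidence interval.

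With one scheduled post-baseline measurement, the only scheduled value that LOCF can carry for an early dropout is the discontinuation value. That value may follow a few days of dosing. In the 20-mg arm, someone who stops in Week 1 has received only 10 mg (Protocol 6.1.1.2), yet is counted in the 20-mg result at Week 6. The estimate thus averages over different durations, and in that arm over different doses, under a label that names one time point.

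Weight is a relevant safety variable here. In the earlier AD/HD trial decreased appetite was reported in 16.9% and nausea in 18.2% of subjects on OPC-64005 (Protocol 2.3). More early dropout on drug than on placebo is plausible: AE discontinuation in that trial was 18/77 on drug against 7/85 on placebo, mostly early in treatment (Protocol 4.3.2).

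**Working it through.** **Plan figures.** The documents state no expected weight change, SD or dropout rate for this analysis, so there is no planned figure to reproduce. Of the two discontinuation rates borrowed from the AD/HD trial, 18/77 = 23.4% agrees with the protocol. 7/85 = 8.2%, where the protocol prints 8.5%; the difference does not matter here.

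**Formula.** Let A and P be the Week 6 changes on active and placebo, a and b the dropout shares, and s the fraction of the 6-week change reached at dropout. Let m be the speed of change in active dropouts relative to active completers. Then

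LOCF difference = [A(1 − a) + a·m·A·s] − [P(1 − b) + b·P·s].

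With P = 0 and m = 1 this becomes A[1 − a(1 − s)], so the proportional shrinkage is a(1 − s).

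**Base case (assumed).** A = −1.0 kg, P = 0, linear change, so s = t/6 for dropout at week t.

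| Active dropout a | t = 1 | t = 2 | t = 3 |
|---|---|---|---|
| 10% | −0.92 | −0.93 | −0.95 |
| 23.4% | −0.81 | −0.84 | −0.88 |

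For example, 0.234 × 5/6 = 0.195 gives −0.81, and 0.10 × 1/2 = 0.05 gives −0.95. The shrinkage runs from 5% to about 20%.

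**Sensitivity to the assumptions** (a = 18/77; b = 7/85 where placebo changes):

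- Effect comes early. With 80% reached by Week 1, 1 − 0.234 × 0.2 gives −0.95. With all of it reached by Week 2, the result is −1.00, no shrinkage.
- Active dropouts at Week 2 lose weight faster than completers, whose Week 6 change is −1.0. At 3 times the speed, 0.766 + 0.234 × 3 × 1/3 gives −1.00. At 6 times, 0.766 + 0.234 × 2 gives −1.23, larger than the completers' difference.
- Both arms gain, placebo 2 kg and active 1 kg, dropout at Week 1: 0.805 − 1.863 = −1.06 against a true −1.0.
- Both arms lose, placebo 1 kg and active 2 kg, dropout at Week 1: −1.610 + 0.931 = −0.68, a larger shrinkage than in the base case.

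The error can therefore be a shrinkage of 5% to 20%, a larger shrinkage, nothing, or a reversal, depending on trajectories that the documents do not give.

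**What the planned tables already show.** Under the analysis windows in SAP 3.4, Week 6 is Days 40 to 50. A discontinuation weight on Day 10 falls in the Week 1 window (Days 2 to 11) of the by-time-point table, so that table keeps observed Week 6 values apart from early ones. It gives no adjusted difference and no interval for the contrast with placebo.

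**The case against.** The strongest reply is that the observed Week 6 contrast is already visible. Changes from baseline are tabulated by arm at each time point, separately from the LOCF endpoint, and threshold counts and a listing are added. A reader might infer from the LOCF model that weight harm would be hidden, or that only carried-forward data are reported. The documents do not support either reading. What the tables lack is the baseline-adjusted difference with its interval.

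A reader might also infer that LOCF must pull the drug effect toward no harm. That does not follow. Subjects who leave with nausea or poor appetite may be those who lost weight fastest, and in that case the shrinkage disappears or reverses.

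Nor can 23.4% be taken as the expected rate here. It comes from an 8-week AD/HD trial that started at 20 mg and moved to 30 mg, and Protocol 4.3.2 cites it as the reason for the lower starting dose in this trial. It counts AE discontinuations only, and the protocol says most, not all, of those events were early.

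Finally, an observed-case model is not free of selection: it drops everyone who left early and could itself understate harm, whereas LOCF keeps every treated subject with a post-baseline weight. This objection stands against making the observed-case result the headline. It does not stand against showing both results.

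**Conclusion.** The point holds in a limited form. The only modelled safety comparison rests on a value that the SAP equates with Week 6 but that, for early dropouts, may reflect days of exposure. It is also the one LOCF analysis listed in SAP 5.3 without an observed-case repeat. The adjusted difference may misstate the 6-week effect. The 5% to 20% attenuation rests on steady change, a flat placebo arm, 10% to 23% active dropout and dropout between Weeks 1 and 3, all of which are assumptions. Neither direction nor size can be settled from the documents.

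The consequence is small: this is an estimation-only safety summary in an exploratory phase 2 trial, with observed descriptive values already planned. The change is worth making because it is cheap and matches the SAP's own practice elsewhere.

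**What to change.** In SAP 9.7.1, and correspondingly in Protocol 9.4.2.5:

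1. Add the same ANCOVA for weight, BMI and waist on observed Week 6 values (Days 40 to 50 window), as SAP 8.2 already does for HAM-D and Apathy Scale.
2. Report it beside the LOCF result and name neither as the headline estimate.
3. Label the LOCF result *last on-treatment value* and remove the Week 6 label. State in SAP 9.7.1 that the existing ANCOVA uses the LOCF dataset, since that section is silent.

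The cost is one further run of an existing model and a change of table label, with no new data. The drawback is that the observed-case estimate describes only subjects who reached Week 6, which is why the two results should be read together.

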9.4.3 Other Analyses

9.4.3.1 Analysis of Demographic and Baseline Characteristics

In each analysis set, descriptive statistics or frequency distribution will be calculated by treatment group and for the overall OPC-64005 group for each demographic and other baseline characteristic.

9.4.3.2 Pharmacokinetic Analysis

For the plasma concentrations of OPC-64005 and OPC-144013, only listings of data will be generated without tabulation.

9.4.3.3 Pharmacodynamic Analysis

No PD analyses are planned.

9.4.3.4 Pharmacokinetic/Pharmacodynamic Analysis

No PK/PD analyses are planned.

9.4.3.5 Pharmacogenomic Analysis

For the CYP2D6 genetic testing results, only listings of data will be generated without tabulation.

9.4.3.6 Exploratory Endpoint Analysis

Not applicable.

9.5 Interim Analysis and Adaptive Design

Not applicable.

9.5.1 Data Monitoring Committee

Not applicable.

10 Supporting Documentation and Operational Considerations

10.1 Appendix 1: Regulatory, Ethical, and Trial Oversight Considerations

10.1.1 Ethics and Responsibility

This trial must be conducted in compliance with the protocol, ICH Good Clinical Practice (GCP) guideline (E6), international ethical principles derived from the Declaration of Helsinki and Council for International Organizations of Medical Science (CIOMS) guidelines, and applicable local laws and regulations. Each trial site will seek approval by an IRB according to regional requirements, and the trial site will provide that documentation to the sponsor. The IRB will evaluate the ethical, scientific, and medical appropriateness of the trial. Further, in preparing and handling the eCRF, IRE and any safety information, the investigator, subinvestigator, and their staff will take measures to ensure adequate care in protecting subject privacy. To this end, a subject ID will be used to identify each subject.

Financial aspects, subject insurance, and the publication policy for the trial will be documented in the agreement between the sponsor and the trial site.

10.1.2 Informed Consent

Informed consent will be freely obtained from all subjects (or their guardian or legally acceptable representative, as applicable for local laws). The ICF will be approved by the same IRB that approves this protocol.

Each ICF will comply with the ICH-GCP guideline (E6), and local regulatory requirements. In support of the site's standard process for administering informed consent, this trial will also allow for electronic informed consent form (eICF) as a tool within applicable regions and trial sites. The eICF utilizes the IRB-approved site-specific ICF to offer subjects an enhanced platform to review and understand their rights as a research subject as well as required trial procedures. When possible, trial sites will have subjects review and sign the eICF prior to starting any trial procedures; however, if local regulations do not allow for use of the electronic format, subjects may continue in the trial utilizing the standard paper and wet ink signature process.

Investigators may discuss trial availability and the possibility for entry with a potential subject without first obtaining consent. However, informed consent must be obtained and documented before initiation of any procedures that are performed solely for the purpose of determining eligibility for this trial, including withdrawal from current medication(s).

Potential subjects are free to refuse entry into the trial, or withdraw from the trial at any time, without justification, and there will be no consequences to their further care.

Once appropriate essential information has been provided and fully explained in layman's language to the subject by the investigator (or a qualified designee), and it has been documented that the subject has had the opportunity to ask questions, the IRB-approved written ICF will be signed and dated by both the subject and the person obtaining consent (investigator or designee), as well as by any other parties required by the IRB. The subject will receive a copy of the signed ICF; the original shall be kept on file by the investigator. Subjects may be asked to sign additional ICFs if the protocol is amended and the changes to the protocol result in additional information that needs to be provided to the subjects, so that they can make a knowledgeable and voluntary decision on continued trial participation. Female partners of male subjects who become pregnant during the course of the trial may be asked to sign additional ICFs in order to collect additional information regarding the nonsubject partner and fetus.

A separate and similar consent process will be followed for PGx testing and FBR. Consent must be obtained before the blood sample is collected. The PGx testing is mandatory, and subjects who do not consent cannot participate in the trial. The FBR is optional and refusal to participate in the FBR does not affect participation in the trial.

